16.2. OTHER EFFICACY VARIABLES

16.2.1. OBSERVED VALUES AND CHANGE FROM BASELINE IN CGI-S SCORE

The CGI-S is a clinician-rated assessment of the subject’s current illness state on a 7-point scale, where a higher score is associated with a greater illness severity. The CGI-S score takes one of the following values: 1 (normal, not at all ill), 2 (borderline mentally ill), 3 (mildly ill), 4 (moderately ill), 5 (markedly ill), 6 (severely ill), 7 (among the most extremely ill patients).

The observed values of CGI-S score at both the DB baseline and the OL baseline, and at each scheduled post-OL baseline extension visit and LOCF, will be summarized descriptively.

Changes from baseline in CGI-S score will be summarized for each scheduled post-OL baseline extension visit and LOCF, based on both the DB baseline and the OL baseline.

CGI-S score will also be summarized by subgroups as listed in section 7.4.

16.2.2. OBSERVED VALUES AND CHANGE FROM BASELINE IN MADRS TOTAL SCORE

The MADRS is a clinician-rated assessment of the subject’s level of depression. The measure contains 10 items that measure apparent and reported sadness, inner tension, reduced sleep and appetite, difficulty

Document: Documentation\SAP

Author: [name]

Version Number:
 Version Date:

Final V1.0
 27FEB2019

Template No: CS_TP_BS016 Revision 4
 Effective Date: 01Apr2016

Reference: CS_WI_BS005

concentrating, lassitude, inability to feel, and pessimistic and suicidal thoughts. Each item is scored in a range of 0 to 6 points, with higher scores indicating increased depressive symptoms. MADRS total score will be calculated by the sum of all 10 item scores. If any item score contributing to the total score is missing, then the MADRS total score will be set to missing.

The observed values of MADRS total score at both the DB baseline and the OL baseline, and at each scheduled post-OL baseline extension visit and LOCF, will be summarized descriptively.

Changes from baseline in MADRS total score will be summarized for each scheduled post-OL baseline extension visit and LOCF, based on both the DB baseline and the OL baseline.

16.2.3. OBSERVED VALUES AND CHANGE FROM BASELINE IN BNSS TOTAL SCORE

The BNSS is a rating scale to measure the current level of severity of negative symptoms in schizophrenia and schizoaffective disorder. The measure is comprised of 13 individual items organized in 6 subscales (blunted affect (items 9, 10, 11), alogia (items 12, 13), avolition (items 7, 8), anhedonia (items 1, 2, 3), asociality (items 5, 6), and distress (item 4)). Each of the items are scored on a Likert-type 7-point scale from 0 - 6, where values of 0 indicates symptom is absent and a value of 6 means the symptom is a severe form. The 13 individual items provide a composite total score (ranging from 0 to 78). In addition BNSS subscale scores will be calculated by summing the item scores under each subscale. If any item score contributing to the total score or a subscale score is missing or rated as "9" (i.e. not rated), then the BNSS total score or the subscale score will be set to missing.

The observed values of BNSS total score at both the DB baseline and the OL baseline, and at each scheduled post-OL baseline extension visit and LOCF, will be summarized descriptively.

Changes from baseline in BNSS total score will be summarized for each scheduled post-OL baseline extension visit and LOCF, based on both the DB baseline and the OL baseline.

A sensitivity analysis for BNSS will be performed where a BNSS subtotal score will be calculated by summing the scores of items 1-6 and 8-13. Item 7 (Avolition: Behavior) is excluded due to several subjects being given a score of '9' for this item when '9' is not a valid rating. Among the 12 items contributing to BNSS subtotal score, if any item is rated as '9', the subtotal score will be set to missing. The same analyses performed on BNSS total score will be repeated on BNSS subtotal score.

16.2.4. OBSERVED VALUES AND CHANGE FROM BASELINE IN CBB COMPOSITE SCORE AND OBSERVED VALUES AND CHANGE FROM OL WEEK 12 IN CSB COMPOSITE SCORE

The Cogstate Brief Battery (CBB) assesses four domains. The Detection test (Psychomotor Function Domain) measures speed of performance. The mean of the log₁₀ transformed reaction times for correct responses is utilized to determine the score. Lower scores correspond to better performance. The Identification test (Attention Domain) also measures speed of performance. The mean of the log₁₀ transformed reaction times for correct responses is utilized to determine the score. Lower scores correspond to better performance. The One Card Learning test (Visual Learning Domain) measures accuracy of performance. The arcsine transformation of the square root of the proportion of correct responses is utilized to determine the domain score. Higher scores correspond to better performance. The One Back test (Working Memory Domain) measures speed of performance. The mean of log₁₀ transformed

Document: Documentation\SAP

Author:

Version Number:
Version Date:

Final V1.0
27FEB2019

Template No: CS_TP_BS016 Revision 4
Effective Date: 01Apr2016

Reference: CS_WI_BS005

Copyright © 2009, 2010, 2012, 2016 Quintiles Transnational Corp. All rights reserved.

The contents of this document are confidential and proprietary to Quintiles Transnational Corp. Unauthorized use, disclosure or reproduction is strictly prohibited.

Statistical Analysis Plan

reaction times for correct responses is used to determine the domain score. Lower scores correspond to better performance.

The Cogstate Schizophrenia Battery (CSB) includes the four tests of the CBB and three additional tests. The Internal Shopping List test (Verbal Learning Domain) measures the total number of correct responses made in remembering the word list on three consecutive learning trials. Higher scores correspond to better performance. The Groton Maze Learning test (Executive Function Domain) measures the total number of errors made in attempting to learn the same hidden pathway across five consecutive learning trials. Lower scores correspond to better performance. The Social Emotional Cognition test (Emotional Cognition Domain) measures the accuracy of performance. Arcsine transformation of the square root of the proportion of correct responses is utilized to determine the domain score. Higher scores correspond to better performance.

A standardized z-score is derived for each test by using the following formula:

$$z = \frac{(\text{Subject score} - \text{Age-adjusted normalization table mean}) \times \text{Multiplicand}}{\text{Age-adjusted normalization table standard deviation}}$$

where

- o multiplicand = -1 when a lower score indicates improved performance (i.e. Detection Test, Identification Test, One Back Test, Groton Maze Learning Test);
- o multiplicand = 1 when a higher score indicates improved performance (i.e. One Card Learning Test, International Shopping List Test, Social Emotional Cognition Test)

The age-adjusted normalization table mean and standard deviation for each test is shown in the table below:

Cogstate Tests	Normative Mean and Standard Deviation	
Detection Test (DET)	2.46	0.09
Identification Test (IDN)	2.66	0.08
One Card Learning Test (OCL)	1.05	0.13
One Back Test (ONB)	2.79	0.10
Internal Shopping List Test (ISL)	25.17	4.30
Groton Maze Learning Test (GML)	34.59	15.85
Social Emotional Cognition Test (SECT)	1.14	0.12

A completion flag and an integrity flag are populated for each test, except for the Internal Shopping List test for which only the completion flag is populated. Test completion refers to criteria that determine whether a sufficient number of responses were recorded during the administration of a test to allow computation of reliable performance measures. Any tests that failed the completion criteria will be excluded from statistical analysis.

Document: Documentation\SAP

Author:

Version Number:
Version Date:

Final V1.0
27FEB2019

Template No: CS_TP_BS016 Revision 4
Effective Date: 01Apr2016

Reference: CS_WI_BS005

Test integrity is a measure of whether a subject performed in accord with the test requirements. When a particular test administration fails to meet criteria for data integrity, this suggests with high probability that the observed score may not reflect the study population or the effect of the compound under investigation. Statistical analysis will be performed both with and without the integrity criteria failures included.

Based on the z-scores of individual tests, a CBB composite score will be derived as the average of the z-scores of the Detection test, Identification test, One Card Learning test, and One Back test. If two or more tests are missing or are excluded from the analysis, the composite score will be set to missing.

Based on the z-scores of individual tests, a CSB composite score will be derived as the average of the z-scores of all seven tests. If three or more components are missing or are excluded from the analysis, the composite score will be set to missing.

The observed values of CBB composite score and the individual standardized scores of the four tests contained in CBB at the DB baseline and the OL baseline, and at each scheduled post-OL baseline extension visit and LOCF, will be summarized descriptively. Changes from baseline in CBB composite score and the individual standardized scores will be summarized for each scheduled post-OL baseline extension visit and LOCF, based on both the DB baseline and the OL baseline.

In addition, the observed values of CSB composite score and the individual standardized scores of the seven tests contained in CSB at Visit 7E (Week 12) and Visit 11E (Week 26) of study 361-202 will be summarized. Change from Visit 7E in CSB composite score and the individual standardized scores at Visit 11E will also be summarized.

16.2.5. OBSERVED VALUES AND CHANGE FROM BASELINE IN UPSA-B TOTAL SCORE

The UPSA-B is a role-play assessment designed to evaluate an individual's functional capacity in Financial Skills and Communication domains of basic living skills. The raw score of the financial subscale ranges from 0 to 11 and the raw score of communication subscale ranges from 0 to 9. Each subscale score is calculated by dividing the raw score by the highest possible raw score of that subscale and then multiplying by 50, so both subscale scores range from 0 to 50. The UPSA-B total score, calculated as the sum of two subscale scores, ranges from 0 to 100. Higher scores reflect better performance. If one or more items contributing to the subscale raw score are missing for a subject at a visit, the UPSA-B total score will be set to missing for that visit.

The observed values of UPSA-B total score at the OL baseline, and at each scheduled post-OL baseline extension visit and LOCF, will be summarized descriptively. Changes from the OL baseline in UPSA-B total score will be summarized at each scheduled post-OL baseline extension visit and LOCF.

16.2.6. RATE OF RELAPSE AND TIME TO RELAPSE

Subjects demonstrating a relapse of psychotic symptoms during the OL extension treatment period will be identified on the relapse population.

Relapse is defined as the earliest occurrence of any of the following:

- An increase in PANSS total score by $\geq 30\%$ from the PANSS total score at clinical response and a CGI-S score ≥ 3

Document: Documentation\SAP

Author:

Version Number:

Final V1.0

Version Date:

27FEB2019

Template No: CS_TP_BS016 Revision 4
 Effective Date: 01Apr2016

Reference: CS_WI_BS005

Copyright © 2009, 2010, 2012, 2016 Quintiles Transnational Corp. All rights reserved.

The contents of this document are confidential and proprietary to Quintiles Transnational Corp. Unauthorized use, disclosure or reproduction is strictly prohibited.

- Re-hospitalization for worsening of psychosis
- Emergence of suicidality, homicidality, and/or risk of harm to self or others

PANSS and CGI-S assessments taken at both scheduled and unscheduled visits will be considered when identifying the relapse event. Occurrence of re-hospitalization for worsening of psychosis will be identified by medical review of the data collected on the Psychiatric Hospitalization CRF page as well as the SAEs prior to database lock. Emergence of suicidality, homicidality, and/or risk of harm to self or others will be identified as outlined in Appendix 3. The evaluation period for relapse will be from the day/time of clinical response to 1 day after the day of the last dose of extension study medication.

The date of relapse is defined as the earliest of: the date of the assessment (based on the QSSTDTC variable in Bracket data) at which the qualifying PANSS and CGI-S data were collected, the date of hospital admission for worsening of psychosis, the date of the assessment (based on the QSSTDTC variable in Bracket data) at which a qualifying C-SSRS event is identified, or the start date of the qualifying adverse event.

The date of clinical response is defined as the date of the PANSS and CGI-S assessments (based on the QSSTDTC variable in Bracket data) which established clinical response.

Time-to-relapse (in days) is defined as the date of relapse – the date of clinical response + 1. Subjects completing/discontinuing from the study without meeting the criteria for relapse will be censored on the day after the last dose of extension study medication. Kaplan-Meier estimates of the median time-to-relapse and the 25th percentile and 75th percentile of time-to-relapse, along with the respective 95% confidence intervals, will be calculated. Kaplan-Meier estimate of the probability of relapse at the end of the OL extension treatment period, and its 95% confidence interval, will also be calculated. The time-to-relapse data will be presented in a Kaplan-Meier curve.

The rate of relapse will be calculated as the proportion of subjects demonstrating a relapse during the OL extension treatment period in the relapse population. The 95% confidence interval for the rate of relapse will also be calculated.

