8.2. Subject Exclusion Criteria

To qualify for participation, subjects must not meet any of the following exclusion criteria:

1. Subject answers "yes" to "suicidal ideation" Item 4 (active suicidal ideation with some intent to act, without specific plan) or Item 5 (active suicidal ideation with specific plan and intent) on the C-SSRS assessment at Visit 7 of Study SEP361-201. Subjects who answer "yes" to this question must be referred to the Investigator for follow-up evaluation.
2. Subject has a clinically significant abnormality including physical examination, vital signs, ECG, or laboratory test at Visit 7 of Study SEP361-201 that the investigator in consultation with the medical monitor considers to be inappropriate to allow participation in the study.
3. Subject has a positive urine drug screen (UDS) or breath alcohol test at Visit 7 of Study SEP361-201.
4. Subject is pregnant or lactating.
5. Subject is at high risk of non-compliance in the Investigator's opinion.

6. Subject is in the opinion of the Investigator, unsuitable in any other way to participate in this study.

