11.4.7.4. Columbia Suicide Severity Rating Scale (C-SSRS)

The C-SSRS is a tool designed to systematically assess and track suicidal adverse events (suicidal behavior and suicidal ideation) throughout the trial. The strength of this suicide classification system is in its ability to comprehensively identify suicidal events while limiting the over-identification of suicidal behavior. The scale takes approximately 5 minutes to administer. The C-SSRS will be administered by a trained rater at the site. Subjects with Type 4 or 5 suicidal ideation during the study will be discontinued from the study and referred to a mental health professional (Posner-2007). For all visits the "Since Last Visit" version of the C-SSRS will be used.

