5.2. RELAPSE POPULATION

The relapse population will include safety population subjects who demonstrated a clinical response to 4 weeks of treatment with SEP-363856. Clinical response is defined as meeting both of the following criteria:

- A decrease in PANSS total score of $\geq 20\%$ from baseline
- A CGI-S score ≤ 4

For subjects who received double-blind SEP-363856 in study 361-201, clinical response will be evaluated using the Week 4 (Visit 7) PANSS and CGI-S data of study 361-201, against the double-blind baseline (see section 6.2). For subjects who received double-blind placebo, clinical response will be evaluated using the Week 4 (Visit 5E) PANSS and CGI-S data of study 361-202, against the double-blind baseline (see section 6.2).

The relapse population will be used for analysis of relapse of psychotic symptoms.

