APPENDIX 3. IDENTIFICATION OF SUICIDALITY, HOMICIDALITY, AND/OR RISK OF HARM TO SELF OR OTHERS

Condition	Data Source	Criteria
Suicidality or Risk of Harm to Self	Adverse events	
 • AEs with preferred term of “Completed suicide” or “Suicide attempt” • Medical review of all AEs contained in the MedDRA SMQ of “Suicide/self-injury (SMQ)”
	C-SSRS	
 • C-SSRS findings of at least one occurrence of suicidal ideation (Item 4 and/or Item 5) or at least one occurrence of suicidal behavior • C-SSRS findings of self-injurious behavior, defined as a “Yes” answer to the following question in the Suicidal Behavior section: Has subject engaged in Non-Suicidal Self-Injurious behavior?
Homicidality or Risk of Harm to Others	Adverse events	
 • AEs with preferred term of “Aggression”, “Anger”, “Antisocial behaviour”, “Belligerence”, “Defiant behaviour”, “Homicide”, “Homicidal Ideation”, “Hostility”, “Physical abuse”, “Physical assault”, or “Violence-related symptom” contained in the MedDRA SMQ of “Hostility/aggression (SMQ)” • AEs with a verbatim term that contains text of “homicid*”, “kill*”, or “murder*”.

Document: Documentation\SAP

Author:

Version Number:

Final V1.0

Version Date:

27FEB2019

Template No: CS_TP_BS016 Revision 4
 Effective Date: 01Apr2016

Reference: CS_WI_BS005

Copyright © 2009, 2010, 2012, 2016 Quintiles Transnational Corp. All rights reserved.

The contents of this document are confidential and proprietary to Quintiles Transnational Corp. Unauthorized use, disclosure or reproduction is strictly prohibited.

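### A C-SSRS finding that predates clinical response can be counted as a day-1 relapse, because the relapse window includes the response visit and that visit's form looks back to the previous one

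*SAP*

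**What the plan says.** SAP 5.2 defines who can relapse: "The relapse population will include safety population subjects who demonstrated a clinical response to 4 weeks of treatment with SEP-363856". Response is judged on PANSS and CGI-S alone, at Visit 7 of SEP361-201 for subjects who had received SEP-363856 and at Visit 5E of the extension for those who had received placebo.

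SAP 16.2.6 sets the clock:

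- Window: "The evaluation period for relapse will be from the day/time of clinical response to 1 day after the day of the last dose" of extension medication.
- Response date: "The date of clinical response is defined as the date of the PANSS and CGI-S assessments" that established response.
- Date of a C-SSRS relapse: "the date of the assessment (based on the QSSTDTC variable in Bracket data) at which a qualifying C-SSRS event is identified".
- Time to relapse: the relapse date minus "the date of clinical response + 1".

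Appendix 3 gives the C-SSRS criteria. One is "C-SSRS findings of at least one occurrence of suicidal ideation (Item 4 and/or Item 5) or at least one occurrence of suicidal behavior"; the other is a positive answer on non-suicidal self-injury. Neither is compared with an earlier visit.

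Protocol 11.4.7.4 and SAP 17.5.4 prescribe the form that asks about the time since the last visit, at every extension visit and from Visit 2 onward in SEP361-201. The C-SSRS is scheduled at both response visits.

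**The concern.** A relapse should come after the response it ends. The C-SSRS at the response visit reports what happened before that visit, yet the SAP gives the finding the date of the visit and includes that date in the window. A suicidal act or self-injury in the days before the response rating can thus become a loss of that response.

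The route by which an event is recorded then decides whether it counts. An adverse event is dated to its own start, so one that began before response falls outside the window. The same event on the C-SSRS form falls inside it. At stake are the relapse proportion, the start of the Kaplan-Meier curve, and whether two programmers would derive the same result from the same data.

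**Working it through.** The plan states no relapse rate or relapse-population size, so there is no figure to reproduce. The check applies the SAP formula to the nominal visit days and then shows the effect of one or more such events.

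**1. Same-day time to relapse.** Time = relapse date − response date + 1.

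- Prior SEP-363856, Visit 7 = Day 1 of the extension: 1 − 1 + 1 = 1 day.
- Prior placebo, Visit 5E = Day 29: 29 − 29 + 1 = 1 day.

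**2. Look-back at Visit 5E.** The previous visit is 4E (Day 22 ± 2), and Visit 5E is Day 29 ± 3. Nominal look-back: 29 − 22 = 7 days. Shortest: 26 − 24 = 2. Longest: 32 − 20 = 12. All of it lies before, or up to, the response visit.

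**3. Which criteria can be met at the response visit.** The PANSS part of the definition cannot, because it is measured against the PANSS at response. Adverse events and admissions carry their own start dates, so only same-day cases are unclear. The C-SSRS is the one source whose assigned date can be later than the event.

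**4. The two groups.**

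- *Prior placebo, Visit 5E.* The visit is within open-label treatment. Item 4 or 5 ideation, suicidal behavior and self-injury would all qualify. Exclusion 1 was applied four weeks earlier and does not bear on this visit. A subject with type 4 or 5 ideation is to be discontinued (Protocol 11.4.7.4), but still meets the SAP 5.2 definition if PANSS and CGI-S show response.
- *Prior SEP-363856, Visit 7.* Exclusion 1 bars entry for ideation item 4 or "Item 5 (active suicidal ideation with specific plan and intent) on the C-SSRS assessment at Visit 7 of Study SEP361-201", so only behavior or self-injury could remain. The window sentence includes this visit. Against that, SAP 16.2.6 confines relapse to the open-label extension treatment period, and SAP 17.5.4 makes this form the open-label baseline, separate from the post-baseline period.

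**5. Size.** Anticipated enrolment is about 180 (Protocol 15.1). The number of responders R is not given; 30%, 50% and 70% of 180 are assumed, so R = 54, 90 and 126. For k day-1 events the rate rises by k/R and the day-1 Kaplan-Meier estimate is 1 − k/R.

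| R (assumed) | 1 event | 3 events | Day-1 Kaplan-Meier, 3 events |
|---|---|---|---|
| 54 | 1.9 points | 5.6 points | 0.944 |
| 90 | 1.1 points | 3.3 points | 0.967 |
| 126 | 0.8 points | 2.4 points | 0.976 |

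Example with R = 90 and an assumed 14 later relapses: 14/90 = 15.6% (Clopper-Pearson 95% CI 8.8 to 24.7). With three day-1 events: 17/90 = 18.9% (11.4 to 28.5). These increments assume that the affected subjects would not have relapsed later; otherwise the rate is unchanged and only the timing moves.

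**6. After the fix.** The earliest scheduled C-SSRS relapse is 8 − 1 + 1 = day 8 for prior SEP-363856 (6 to 10 with the visit window). For prior placebo it is 57 − 29 + 1 = day 29 (54 − 32 + 1 = 23 to 60 − 26 + 1 = 35).

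**The case against.** The best defence is that the SAP already excludes these findings. The window opens at a day or a time, and response needs both PANSS and CGI-S. In the Visit 1E order the C-SSRS is fourth and CGI-S fifth; the Visit 5E list has the same sequence, though it is not labelled an order. If response is complete only at CGI-S, the C-SSRS precedes the window. The criterion also speaks of emergence, which suggests something new. For Visit 7 there is more: the restriction to the open-label treatment period, the baseline status of that form, evening dosing, and SAP 6.4, which names only unscheduled data collected after open-label baseline as feeding relapse identification.

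Most of this stands for Visit 7, where the text conflicts and no single reading is settled. It does not settle Visit 5E. Response and relapse are defined there by dates, an anchor on PANSS instead of CGI-S would keep the C-SSRS in, and emergence is to be identified through Appendix 3, which has no new-onset condition.

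It is also fair that a finding at Visit 5E may reflect an event on open-label drug, so calling it a false relapse is a judgment. The narrower point survives: the event is misdated relative to the response, and an adverse-event record of it would be treated differently.

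**Conclusion.** The point holds, at low severity. On the SAP's date-based definitions, a qualifying event before response can be counted as a day-1 relapse. This is clear at Visit 5E and unresolved at Visit 7. The likely effect is zero to a few subjects, each worth about 0.8 to 1.9 points under the assumed 54 to 126 responders. Neither that range nor any event frequency comes from the documents. Relapse is an exploratory secondary objective, and no hypothesis is tested (Protocol 4.4, 5.2).

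A reader might infer more, and the documents do not support it:

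- *That exclusion 1 must match Appendix 3.* An entry criterion and an outcome definition serve different purposes and need not share a threshold. Investigator judgment (exclusion 6) also applies, and the withdrawal rules of SEP361-201 are not in these documents.
- *That affected subjects were never free of the relapse criteria.* An event days earlier does not show the subject's state at response.
- *That these subjects should leave the relapse population.* They meet the response definition; the problem is the dating of one finding.
- *That the Kaplan-Meier curve will drop on day 1.* It can, but no such event may occur.

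**What to change.** In SAP 16.2.6, state that C-SSRS findings count toward relapse only from the first C-SSRS assessment after the response visit, and that adverse events or admissions on the response date count only if they start after the response assessments. The next form covers the interval since the response visit, so later events reported on it are still captured.

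List all subjects with a qualifying C-SSRS finding at the response visit, by prior treatment group, and optionally show the relapse rate with them counted.

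The cost is a sentence or two of SAP text, a date condition in the program and one listing. The downside is that the relapse count may fall slightly, a direction that favours the drug. A prior-placebo subject discontinued for ideation found at Visit 5E, with no other qualifying event, would be censored the day after the last dose instead of counted as a relapse. The listing and the optional second rate keep that visible.
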